10.2.2 Analysis Plan

The correlation between the independent variable $TDD_{insulin}$ (averaged over 7 days prior to each STUDY B-C visit) and the GIR over the last 30 minutes of the clamp will be determined. Several other explanatory variables could confound this bivariate analysis, however. For example, confounding variables might include treatment order, hyperglycemia, hyperlipidemia, or measures of glycemic variability. For this reason, as with STUDY 1-5, I will use multivariable linear regression analysis to account for the effect of these potential confounders.

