Iatrogenic hyperinsulinemia's contribution to endothelial dysfunction early in the course of T1DM is uncharacterized. Impaired endothelial function has been consistently observed in prepubertal,(29) midpubertal,(6) and postpubertal pediatric patients,(8) as well as young(30) and middle-aged(7) adults with T1DM. Several lines of research suggest insulin may exert beneficial vascular effects by increasing endothelial nitric oxide (NO) synthase gene expression(31) and activity(32, 33) and stimulating NO release and vasodilation.(34-36) On the other hand, hyperinsulinemia may exert detrimental vascular effects by amplifying mitogenic activity of growth factors, increasing expression of endothelial adhesion molecules, and enhancing monocyte adhesion to the endothelium.(34, 37, 38) Induction of hyperinsulinemia in healthy subjects to concentrations matching basal insulin levels typically seen in T1DM drastically diminished flow-mediated dilation (FMD), a frequently-used technique to quantify endothelial function.(39) Further study suggested this effect was mediated *independent of insulin sensitivity*.(34) Thus, my primary outcome in Aim 2 will determine how much clinically driven changes in peripherally delivered insulin doses modify brachial artery endothelial function during the early course of T1DM. As a secondary objective of Aim 2, I will use the contrast-enhanced ultrasound (CEUS) technique(40) to measure insulin-induced microvascular recruitment in adult participants.

Therapies to lower hyperinsulinemia-mediated IR and endothelial dysfunction in T1DM are limited. To date, no study has attempted to improve IR or endothelial dysfunction by lowering the total daily dose of insulin (TDD_{insulin}). The dearth of these studies is partially related to concern that lowering TDD_{insulin} would worsen hyperglycemia. A diet that is lower in carbohydrates, however, is one approach to safely lower TDD_{insulin} without raising glycemia. Thus, in Aim 3, we will conduct a 2x2 crossover intervention study testing whether the reduction in TDD_{insulin} over a one-week low-carbohydrate diet (LCD) intervention will result in improved insulin sensitivity compared with one-week standard carbohydrate diet (SCD).

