10.0 Statistical Considerations

10.1 STUDY 1-7 (Aims 1-2)

10.1.1 Sample Size Justification

My accrual goal is to obtain an adequate number of participants within both the T1DM SUBSTUDY (STUDY 1-3) and CONTROL SUBSTUDY (STUDY 4-7) to ensure greater than 80% statistical power ($1-\beta$) for a two-sided α -level of 5% for each specific aim's primary outcome. The sample size calculations used the best-available previously published descriptions of insulin sensitivity(28, 105) and %FMD(7, 30, 106-108) in T1DM. Table 7 summarizes these calculations.

Table 7: Key parameters for sample size calculations for T1DM and CONTROL substudies. n , δ , $1-\beta$, σ , and r represent the sample size, the expected minimum difference, statistical power, overall standard deviation, and longitudinal correlation, respectively, for each key outcome. * indicates calculations based on preliminary data as previously described. [†] The detectable differences for GIR of 1.3 to 2.2 mg/kg/min represent a 20% to 21% change in outcomes. [‡] The detectable differences for %FMD of 2.2% to 4.3% represent a 25% to 39% change in outcomes.

Aim	T1DM Substudy					Control Substudy						
	Key Outcome for Power Calculation	n	δ	$1-\beta$	σ	r	Key Outcome for Power Calculation	n	δ	$1-\beta$	σ	r
1	GIR between STUDY T ^{LO} vs. T ^{HI} in mg/kg/min	20	1.3	0.88	2.7	0.79	GIR between STUDY C ^{BOTH} vs. C ⁰ in mg/kg/min	20	2.2	0.92	3.5	0.79
2	%FMD between STUDY T ^{LO} vs. T ^{HI}	20	2.2%	0.88	4.3%	0.83	%FMD between STUDY C ^{BOTH} vs. C ⁰	20	4.3%	0.83	3.7%	0.83

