10.1.2 Analysis Plan

The correlation between the independent variable TDD_{insulin} (averaged over 7 days prior to each STUDY visit) and the key dependent variable for each objective will be determined: GIR in Aim 1; %FMD and MVR in Aim 2. Several other explanatory variables could influence each specific aim's key dependent variable, however. For example, confounding variables might include hyperglycemia, hyperlipidemia, or the dependent variables in each aim could affect one another (e.g. insulin resistance could affect endothelial dysfunction). For this reason, I will use multivariable linear regression analysis to account for the effect of potential confounders, which include age, T1DM duration, glycemia (both from both CGM over 7 days and HbA1c), lipidemia (i.e. lipoprotein subclass sizes and particle concentrations), NEFA concentration, hypertension, BMI, body composition, and estrogen level.

The study accrual of 40 participants provides 3 to 4 degrees of freedom for a multivariable linear regression analysis. (i.e. TDD_{insulin} and 3 additional independent variables can be included in an adequately-powered model). To quantify the effect of potential confounders, unadjusted and adjusted linear regression models will be fit and compared for each Aim's primary outcome (GIR and %FMD). I will analyze changes in β -coefficients between unadjusted and adjusted models for scientifically significant differences.

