10.2 STUDY B-C (Aim 3)

10.2.1 Sample size justification

My accrual goal for STUDY B-C is to have a sufficient sample size to conduct multivariable linear regression with 4 degrees of freedom to quantify the effect of the independent variable, mean $TDD_{insulin}$, on the dependent variable, GIR during the last 30 minutes of the clamp study. At a minimum, 10 participants are needed per degree of freedom to conduct this analysis, thus, we will study 30 participants with T1DM and 10 control participants who are otherwise healthy.

Based on Del Prato et al.,(27) I anticipate participants completing the SCD arm will not see a change in GIR during the last 30 minutes of the clamp study compared to baseline, but will see an increase in GIR of at least 0.6 mg/kg/min after completing the LCD arm. This study also suggests the pooled standard deviation of GIR will be 0.8 mg/kg/min. If the true difference in the Δ GIR between LCD and SCD arms for the 30 T1DM participants is 0.6 mg/kg/min, we will be able to reject the null hypothesis that the difference is zero with probability (power) 0.976. The type 1 error probability associated with this test of this null hypothesis is 0.05.

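### The Aim 3 analysis plan omits the LCD-SCD comparison that the sample size powers at 0.976, and gives no method for handling two visits per person

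*Combined protocol and SAP*

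**What the plan says.** STUDY B-C is a crossover in which section 5.3 randomises the order of the two diets, and each participant is clamped once after each diet (section 6.2).

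Section 10.2.1 offers two sample-size arguments. The first is a count of participants sufficient "to conduct multivariable linear regression with 4 degrees of freedom", at ten per degree of freedom, which leads to 30 T1DM and 10 control participants. The second is a hypothesis test: a true LCD-SCD difference of 0.6 mg/kg/min in the 30 T1DM participants, "pooled standard deviation of GIR will be 0.8 mg/kg/min", type 1 error 0.05, and the statement that "we will be able to reject the null hypothesis that the difference is zero with probability (power) 0.976".

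Section 10.2.2 relates insulin dose "averaged over 7 days prior to each STUDY B-C visit) and the GIR over the last 30 minutes of the clamp will be determined". It then calls for multivariable linear regression, for which "confounding variables might include treatment order, hyperglycemia, hyperlipidemia, or measures of glycemic variability". It points back to the approach for STUDY 1-5. Section 10.1.2, which describes that approach, says "unadjusted and adjusted linear regression models will be fit and compared" and is also silent on repeat visits.

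Insulin dose is managed by the participant as the endocrinologist prescribes (section 6.2.2). Section 1.0 describes Aim 3 as "testing whether the reduction in TDD_{insulin} over a one-week low-carbohydrate diet (LCD) intervention will result in improved insulin sensitivity" relative to the standard diet. Section 10.2.4 allows stopping at z = 2.80 on each aim's primary analysis.

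**The concern.** A statistician following 10.2.2 as written would not compare the diets. The only randomised factor has no term in the model, and the exposure that does have a term is chosen by participants and their physicians.

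Three things follow. The quoted power belongs to an analysis that 10.2.2 does not contain. The stopping bound has no identified Aim 3 test, since 10.2.1 supplies two candidates. And nothing says that either analysis is made within participants. If the 60 T1DM visits are pooled, the dose slope mixes a within-person contrast, which the diet moves, with a between-person contrast, in which people with more insulin resistance may simply need more insulin. A negative slope could then appear with no diet or dose effect and be read as benefit from lowering insulin. Clustered standard errors would not help, because the problem is confounding between people rather than a variance that is too small.

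Three of the four example adjusters (hyperglycemia, hyperlipidemia, glycemic variability) can also be changed by the diet. That is a problem for any estimate of the diet effect.

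**Working it through.** **1. Reproducing 0.976.** Inputs from 10.2.1: n = 30, difference 0.6, SD 0.8, alpha 0.05. Section 10.2.4 gives the two-sided convention. For a paired t-test the noncentrality is 0.6 / (0.8/√30) = 4.11.

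- Paired, 29 df: 0.978 (a central-t approximation gives 0.976). With a period term, 28 df: 0.977.
- Two-sample, 30 per arm: 0.81. Two-sample, 15 per arm: 0.51.

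Only the paired diet contrast matches. It requires 0.8 to be the SD of the within-person difference, whereas the text calls it a pooled SD of GIR.

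**2. What if 0.8 is something else?** If 0.8 is the SD at one visit, the SD of the difference is 0.8√(2(1−r)). Section 10.2 gives no r for Aim 3.

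- r = 0: SD 1.13, power 0.80
- r = 0.3: SD 0.95, power 0.92
- r = 0.5: SD 0.80, power 0.978
- r = 0.79: SD 0.52, power above 0.99

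Table 7 in 10.1.1 lists "statistical power, overall standard deviation, and longitudinal correlation, respectively, for each key outcome". For GIR in the T1DM substudy it gives SD 2.7 and r 0.79. Then 2.7√(2 × 0.21) = 1.75, and power for 0.6 at n = 30 is 0.44. The same formula returns Table 7's own row (n = 20, difference 1.3): 0.883 against a stated 0.88.

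**3. What pooling can do with no true effect.** From the documents: dose on LCD one-third lower (Figure 7 legend) and GIR SD 0.8. Assumed: SCD dose 0.6 with SD 0.15 units/kg/day, T1DM only, and a correlation c between dose and a person's underlying GIR.

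The bias can be seen by hand at c = −0.4, r = 0.5. The SD of underlying GIR is 0.8√0.5 = 0.566. Dose SD is 0.15 on SCD and 0.10 on LCD, so the average covariance is −0.4 × 0.125 × 0.566 = −0.0283. Pooled dose variance is (0.0225 + 0.0100)/2 + 0.1² = 0.02625, where 0.1 is half the mean dose difference of 0.2. The expected slope is −0.0283/0.02625 = −1.08. Over a dose drop of 0.2 this reads as a gain of 0.22 mg/kg/min, about a third of the planned 0.6, with no effect present.

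Simulated rejection rates (%) at nominal 5%, 20,000 to 40,000 trials per cell:

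| Analysis | c = 0 | −0.1 | −0.2 | −0.3 | −0.4 |
|---|---|---|---|---|---|
| Pooled, r 0.5 | 6 | 8 | 14 | 24 | 38 |
| Pooled, r 0.79 | 7 | 10 | 19 | 35 | 55 |
| Pooled, clustered SE, r 0.5 | 6 | 8 | 14 | 23 | 38 |
| Adjusted for order and two covariates, r 0.5 | 6 | 7 | 10 | 15 | 24 |
| Random intercept only, r 0.5 | 6 | 7 | 9 | 13 | 20 |
| Paired LCD-SCD | 5 | 5 | 5 | 5 | 5 |
| Dose, fixed participant effect | 5 | 5 | 5 | 5 | 5 |

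The two covariates in the adjusted row are assumed to correlate −0.5 and −0.3 with underlying GIR.

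**4. With a true diet shift of 0.6 (r 0.5).** Pooled regression has power 0.42 at c = 0. It rises to 0.93 at c = −0.4, and that rise is confounding. The paired test has about 0.98. Dose with a fixed participant effect has 0.97 but, without a diet term, cannot separate dose from diet. Regressing change in GIR on change in dose with an intercept does separate them, but power is only 0.165 if dose truly acts at −3 mg/kg/min per unit/kg/day (−3 × −0.2 = 0.6).

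**The case against.** The strongest reply is that dose is the intended exposure. Sections 2.0, 4.0 and 10.2.1 all treat insulin dose as the variable of interest and diet as the means of moving it, and the regression has its own sample-size argument, separate from the 0.976. On that reading, making diet primary is a reviewer's preference. It stands that the dose question is legitimate and should be kept. It does not remove the gap: 10.2.1 states a diet test that 10.2.2 does not carry, and diet is the only randomised and powered contrast.

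Second, silence is not prohibition: 10.2.2 gives its covariates as examples, and section 4.0 relies on the crossover to reduce variance. That is correct. The within-participant model is unspecified rather than excluded, but no section supplies it.

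Third, the error rates rest on assumed inputs. This stands. With no between-person correlation, pooling costs only a point or two. Defining the correlation against observed GIR gives about 65% at −0.4. Assuming a between-person slope of −3 with the SD of the paired difference held at 0.8 gives 82% at r 0.5 and 50% at r 0.79. If dose acts at −3 both between and within people, pooled power is 0.991. The direction of the risk is plausible; the exact percentages should carry little weight.

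Fourth, the 0.44 borrows an SD from newly diagnosed participants in another substudy, and 10.2.1 takes its 0.8 from a different source. That is fair; it is a reason to reconcile the two figures, not a finding that 30 is too few.

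Finally, the table leaves out the 10 controls. If they enter at dose zero with a group term, the rates hardly change (6% at c = 0, 39% at −0.4). Without a group term, and with equal mean GIR, they are 9% and 19%. Having no insulin dose, they add nothing to a within-person dose slope.

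Adjusting for glycemia is reasonable for the dose question; the objection to it applies only to the diet effect.

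**Conclusion.** The concern holds and should be fixed before analysis. The main defect needs no simulation: 10.2.1 powers a paired LCD-SCD contrast, 10.2.2 specifies only a regression on unassigned dose with no diet term or participant effect, and 10.2.4 therefore has no identified Aim 3 test. The 0.976 is sound on its own inputs for the paired test if 0.8 is the SD of the paired difference; it says nothing about the regression. If visits are pooled, false-positive rates of 6% to 38% (r 0.5) or 7% to 55% (r 0.79) are possible over assumed dose-GIR correlations from 0 to −0.4. The documents give no value for that correlation, so these figures are illustrative.

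**What to change.** In section 10.2.2:

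1. State the powered test as the primary analysis: the within-participant LCD minus SCD difference in GIR in T1DM participants, from a model with diet, period, sequence and a participant effect, not adjusted for anything measured after the diet starts. State that the bound in 10.2.4 applies to this test.
2. Keep the insulin-dose analysis for the mechanistic question, fitted within participants: a fixed participant effect, or change in GIR against change in dose. A random intercept alone is not enough. Say whether a diet term is included, and report the result as an association. If it is to be a co-target, give it its own power statement.
3. In 10.2.1, state that 0.976 is conditional on 0.8 being the SD of the paired difference, and reconcile that with Table 7 (SD 2.7, r 0.79).

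This is wording only. All the data are already planned and no participants are added. Power of the primary test stays at 0.977 with the period term if 0.8 is the SD of the paired difference. The change does not settle whether 30 is enough; that depends on item 3.

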10.2.3 Recruitment goals

Based on Yki-Jarvinen et al., I anticipate a 15% drop out rate.(28) Thus, 35 T1DM and 12 control participants will be enrolled to achieve the recruitment goal of 30 T1DM and 10 control participants completing the study.

10.2.4 Interim assessment

I will make one interim assessment after reaching one-half of the target accrual for the T1DM and control participants. Using Obrien-Fleming bounds for each aim's primary analysis with a two-sided test with α -level of

5%, a critical z-value of 2.80 (corresponding to a p-value of 0.0051) will be used to end the study at interim analysis. We will analyze our study's variance and adjust the sample size if needed.

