10.1.4 Interim assessment

I will make one interim assessment after reaching one-half of the target accrual for the longitudinal, cross-sectional, and control studies. Using Protocol Version #:6

Obrien-Fleming bounds for each aim's primary analysis with a two-sided test with α -level of 5%, a critical z-value of 2.80 (corresponding to a p-value of 0.0051) will be used to end the study at interim analysis. We will analyze our study's variance and adjust the sample size if needed.

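### An efficacy stop at half accrual would leave about 20 participants, enough for 2 of the adjusted model's 4 degrees of freedom by the plan's own minimum

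*Combined protocol and SAP*

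**What the plan says.** **Accrual target.** Section 10.2.1 derives the Aim 3 sample size from the regression. The goal is to "conduct multivariable linear regression with 4 degrees of freedom to quantify the effect of the independent variable", mean total daily insulin dose, on GIR. It adds: "At a minimum, 10 participants are needed per degree of freedom to conduct this analysis". Hence "we will study 30 participants with T1DM and 10 control participants who are otherwise healthy". A separate power statement of 0.976 covers the LCD-SCD contrast in the 30 T1DM participants. For Aims 1-2, section 10.1.2 says: "The study accrual of 40 participants provides 3 to 4 degrees of freedom", meaning insulin dose plus three further covariates at most.

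**Interim rule.** Section 10.2.4 plans one look at half accrual: "I will make one interim assessment after reaching one-half of the target accrual for the T1DM and control participants". It continues: "Using Obrien-Fleming bounds for each aim's primary analysis with a two-sided test" at 5%, "a critical z-value of 2.80 (corresponding to a p-value of 0.0051) will be used to end the study at interim analysis". Section 10.1.4 repeats the rule for Aims 1-2; there too the bound "will be used to end the study at interim analysis". In both sections the only other interim action is to review the variance and adjust the sample size if needed.

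**Analysis.** Sections 10.1.2 and 10.2.2 relate insulin dose to the outcome and use multivariable regression to handle confounders. Section 2.0 frames all three aims as quantifying an effect, and for Aim 3 it asks for the reduction in insulin resistance adjusted for covariables.

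**The concern.** The target of 40 and the stopping rule serve different purposes. The target is sized for an adjusted estimate, whereas the stop is triggered by rejecting a null hypothesis, which can happen with far fewer participants. Once the bound is crossed, the plan as written ends the study at about half the number that it calls the minimum for its regression.

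Two things are then lost. The adjusted coefficient, which is what the aims promise, is estimated below the plan's own planning minimum. In addition, an estimate taken because it crossed a high bound tends to be too large, which matters when the aim is to say how much.

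**Working it through.** **1. Reproduce the plan's figures.**
- Bound: 2 × (1 − Φ(2.80)) = 0.0051, as stated.
- Aim 3 power (section 10.2.1: difference 0.6, SD 0.8, n = 30, α = 0.05). As a paired t-test, the noncentrality is 0.6/0.8 × √30 = 4.108 with 29 df, and power is 0.978 against the stated 0.976. A two-sample calculation with 30 per arm gives 0.828 and does not match. So 0.8 is being used as the SD of the within-person difference.

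**2. Size at the interim.**
- Aim 3: 30/2 + 10/2 = 15 + 5 = 20.
- Aims 1-2: 20/2 + 20/2 = 10 + 10 = 20.
- Counting enrolment instead for Aim 3: (35 + 12)/2 = 23.5, and less 15% dropout this is again about 20 completers.

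**3. Degrees of freedom by the plan's rule.**
- Full accrual: 40/10 = 4.
- Half accrual: 20/10 = 2, that is, insulin dose plus one covariate.
- T1DM participants only in Aim 3: 15/10 = 1.5.

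**4. Chance of stopping in Aim 3**, assuming that the monitored test is the paired GIR contrast in 15 T1DM participants. Noncentrality = 0.6/0.8 × √15 = 2.905.
- Normal statistic against 2.80: P(Z > 2.80 − 2.905) = 0.54.
- p < 0.0051 read from t with 14 df (critical value 3.32): 0.38.
- Sensitivity: if 0.8 were instead a per-visit SD, the SD of the difference would be 0.8 × √(2(1 − r)), with r not stated for Aim 3. For illustration, r from 0 to 0.79 gives 0.23 to 0.95 on the z bound. Of the correlations tried (0, 0.3, 0.5 and 0.79), only r = 0.5, which makes the SD of the difference 0.8, returns the stated power.

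**5. Estimate among stopped Aim 3 trials (z scale).** SE = 0.8/√15 = 0.2066. The mean of Z given Z > 2.80 is 2.905 + φ(0.105)/0.542 = 3.637. Times SE, this is 0.75 against a true 0.60, an excess of about 25%.

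**6. Aims 1-2 (Table 7).** SD of the paired difference = σ√(2(1 − r)); power by paired t at n = 20.

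| Row | SD of difference | Power from inputs | Stated power |
|---|---|---|---|
| T1DM GIR | 1.75 | 0.88 | 0.88 |
| Control GIR | 2.27 | 0.98 | 0.92 |
| T1DM %FMD | 2.51 | 0.96 | 0.88 |
| Control %FMD | 2.16 | > 0.999 | 0.83 |

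Only T1DM GIR reproduces. At n = 10 its noncentrality is 1.3/1.75 × √10 = 2.35, and its crossing chance is 0.33 on z > 2.80, or 0.18 if p < 0.0051 is read from t with 9 df (critical value 3.68).

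**The case against.** **The monitored test is not named.** The bound applies to each aim's primary analysis, which sections 10.1.2 and 10.2.2 describe as a regression. If the monitored quantity is the regression coefficient, the 0.54 does not apply, and the documents give no basis for any stopping probability. A stop would then also mean that the regression had been run and had crossed. This stands, so the probabilities above are conditional. The fall from 4 df to 2 does not depend on it.

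**A 4-df model can still be fitted to 20 people.** Each contributes two visits in Aim 3 and three or four in Aims 1-2. This is right, so it would be too strong to say that the model cannot be fitted. But the plan's minimum counts participants, not visits, and at 20 the model falls below it and loses precision.

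**An O'Brien-Fleming look is standard, and stopping spares participants further procedures.** That is true, and it is the real cost of removing the stop. The plan does not weigh it against the adjusted estimate for which it sized the study.

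**Two stronger readings are tempting.**
- A reader might infer from Table 7 that an early stop in Aims 1-2 is almost certain, because the control %FMD inputs give a crossing chance above 0.99 at n = 10. Those inputs imply power above 0.999 where the table states 0.83, so the row cannot carry that conclusion. Working back from the four stated powers gives about 0.27 to 0.39 per outcome on the z bound. The chance of at least one crossing is then about 0.79 if all four were independent, an assumption that the documents do not support for outcomes measured in the same people.
- A reader might also infer that a crossing on %FMD would cut off GIR, or the reverse. Section 10.1.4 can be read that way, but it can equally mean that only the component concerned ends. Section 10.2.4 offers no basis for it, since sections 10.2.1 and 10.2.2 name only GIR for Aim 3.

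**Conclusion.** The point holds. As written, the plan can end at about 20 participants, which by its own rule supports 2 of the 4 df that the adjusted regression needs, with no reduced model and no provision to continue accrual. This follows from the text and needs no assumption about effect size.

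How likely a stop is depends on the monitored test. For Aim 3, taking the powered paired GIR contrast with a difference of 0.6 and an SD of difference of 0.8, the chance is 0.54 on z or 0.38 on t, and stopped trials overstate the effect by about a quarter (z scale). For Aims 1-2 the only usable figure is T1DM GIR: 0.33 on z or 0.18 on t. No overall stopping probability for Aims 1-2 can be taken from Table 7 until its other three rows are reconciled.

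**What to change.** In sections 10.1.4 and 10.2.4, delete the efficacy stop. Keep the single interim assessment as a check of pooled variance only, with no comparison of conditions and no reduction of the target below the planned accrual. Complete that accrual and run the final tests at the stated two-sided 0.05; no alpha is then spent at the interim.

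Requiring every primary outcome to cross before stopping would not solve the problem, because a stop under that rule still leaves about 20 participants.

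The change is to wording only, and the target of 40 is unchanged. The cost is that a possible early finish is given up and the remaining planned participants undergo the study procedures.

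### STUDY B-C can stop for efficacy at 20 participants, half the minimum that the plan sets for its own 4-df regression, with no correction of the estimate after a stop

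*Combined protocol and SAP*

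**What the plan says.** For STUDY B-C (Aim 3), section 10.2.1 gives the accrual goal as "to have a sufficient sample size to conduct multivariable linear regression with 4 degrees of freedom", relating mean total daily insulin dose to GIR. It adds a floor: "At a minimum, 10 participants are needed per degree of freedom to conduct this analysis". From this it concludes that "we will study 30 participants with T1DM and 10 control participants who are otherwise healthy". The same section then gives a power statement for a different quantity, the LCD-SCD difference in the 30 T1DM participants: difference 0.6 mg/kg/min, SD 0.8, power 0.976, type 1 error 0.05.

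Section 10.2.4 sets the interim: "I will make one interim assessment after reaching one-half of the target accrual for the T1DM and control participants". The test is described as "Using Obrien-Fleming bounds for each aim's primary analysis with a two-sided test with" an alpha of 5%, and "a critical z-value of 2.80 (corresponding to a p-value of 0.0051) will be used to end the study at interim analysis". The same paragraph allows a variance review and a change of sample size.

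For Aims 1-2, section 10.1.2 says "The study accrual of 40 participants provides 3 to 4 degrees of freedom for a multivariable linear regression analysis". Section 10.1.4 uses the same bound at half accrual, and there too it "will be used to end the study at interim analysis".

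No section requires accrual to reach 40 before a stop, reduces the model at or after the interim, or gives an adjusted estimate after a stop.

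**The concern.** The two sections of the Aim 3 plan conflict. One derives 40 participants from a stated minimum for the regression; the other allows the study to end with half that number. By the plan's own rule, the regression fitted after a stop would be too small for its 4 df.

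This matters because the aims ask about size: section 2.0 sets out to quantify contributions and to determine how much an intervention can reduce insulin resistance. The product is an adjusted estimate, not only a yes or no. A stop triggered by a large interim result has two effects on that product. It weakens the adjustment, and it selects for estimates that are too high.

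**Working it through.** **1. The plan's size rule.** 10 participants per df × 4 df = 40 = 30 T1DM + 10 controls. The plan's figure is reproduced.

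**2. Size at the interim.** 30/2 + 10/2 = 15 + 5 = 20. Participants per df: 20/4 = 5, against a minimum of 10. Df supported under the rule: 20/10 = 2. Counting participants, a model with four predictors and an intercept has 20 − 5 = 15 residual df, against 40 − 5 = 35 at full accrual.

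**3. The bound.** A two-look O'Brien-Fleming design at half information, two-sided 5%, gives an interim z of 2.797 and a final z of 1.977. The two-sided p for z = 2.80 is 0.0051. The stated bound is correct.

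**4. The planning inputs.** Section 10.2.1 gives a difference of 0.6, SD 0.8 and n = 30. If 0.8 is the SD of the within-person difference, the paired t-test has noncentrality (0.6/0.8)√30 = 4.11 and power 0.978, against 0.976 stated. Reading 0.8 as a single-visit SD does not reproduce it: SD 0.8√2 for the difference gives 0.802, and a two-sample test with 30 per arm gives 0.828. I therefore take 0.8 as the SD of the difference.

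**5. Chance of a stop and mean estimate after it, Aim 3 paired contrast.** With 15 pairs the standard error is 0.8/√15 = 0.207 and the expected z is 0.6/0.207 = 2.90, just above the bound. With known SD, P(stop) = Φ(2.90 − 2.80) = 0.54, and the estimate must exceed 2.80 × 0.207 = 0.58 to cross. The plan does not say how 2.80 is applied in a small sample, so three versions are shown (simulation, 400,000 interims each).

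| Rule at 15 pairs, true difference 0.60 | P(stop) | Mean estimate after a stop | Ratio to truth |
|---|---|---|---|
| z with known SD above 2.80 | 0.54 | 0.75 | 1.25 |
| t-statistic above 2.80 | 0.56 | 0.73 | 1.22 |
| t-test p at most 0.0051 (critical t 3.32, 14 df) | 0.39 | 0.78 | 1.29 |

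Averaged over stopping and continuing to 30 pairs, the mean estimate is 0.634 to 0.641: 0.634/0.60 = 1.06 and 0.641/0.60 = 1.07.

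If the true difference were 0.3 (an assumption), a stop would occur in 6 to 13% of studies, with a mean estimate of 0.60 to 0.68, about 2.0 to 2.25 times the truth.

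**6. If the bound tests a regression slope instead.** The documents give no effect size for the slope. Assuming final power between 0.80 and 0.976, a normal approximation at half information gives P(stop) of 0.21 to 0.49 and a mean estimate after a stop of 1.70 to 1.29 times the truth.

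**7. Aims 1-2, T1DM GIR contrast.** Table 7 gives 1.3, SD 2.7, r 0.79, n = 20. SD of the difference = 2.7 × √(2(1 − 0.79)) = 1.75. At n = 20 the noncentrality is (1.3/1.75)√20 = 3.32 and paired t power is 0.88, as Table 7 states. At 10 pairs the same three rules give:

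| Rule at 10 pairs, true difference 1.3 | P(stop) | Mean estimate after a stop |
|---|---|---|
| z with known SD above 2.80 | 0.33 | 1.91 |
| t-statistic above 2.80 | 0.38 | 1.77 |
| t-test p at most 0.0051 | 0.18 | 1.93 |

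The estimate after a stop is 36 to 49% too high. Averaged over both outcomes it is 1.36 to 1.40, or 4 to 8% too high.

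**The case against.** **The bound may not test the regression.** A reader might infer that 10.2.4 applies the 4-df regression at 20 participants. The text refers only to the aim's primary analysis. Sections 2.0 and 10.2.2 point to the regression, but the only Aim 3 test given an effect, power and type 1 error is the LCD-SCD difference, and Table 7 also uses within-person contrasts. This stands: the text is ambiguous, and the stop probabilities of 0.39 to 0.56 belong to the paired contrast. The conflict remains on either reading, because a stop leaves the regression at 20 participants.

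**The adjusted analysis would survive.** A reader might infer that a stop removes it. It does not: the model can be fitted with 15 residual df counting participants, and two visits each give 40 correlated observations. But the rule in 10.2.1 counts participants, so the model is weaker and below the stated minimum.

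**Aims 1-2 are not the same case.** The minimum per df is stated only in 10.2.1. Section 10.1.2 says what 40 participants provide and sets no minimum for fitting. Half accrual there gives up to 10 × 3 + 10 × 4 = 70 repeated measurements. Section 10.1.4 also does not say whether one aim or both must cross; if both, a stop is less likely than the T1DM GIR figures suggest.

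**Bias after a stop is a general property of efficacy stopping.** This is true, and O'Brien-Fleming is a conservative early bound. The excess is an average over studies that stop, not a certainty in any one, and the overall excess is much smaller. But a reader of a stopped study sees the conditional estimate, and the plan provides no correction.

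**Early stopping spares participants.** It might be argued that stopping early protects no one because exposures are short. The documents contradict that. Later participants would be spared two clamps and up to 254 mL of blood drawn (section 7.3), insulin exposure in STUDY 4-7 controls (section 7.1), and, for adolescents, procedures rated above minimal risk (section 7.5.2).

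**Conclusion.** The point holds for STUDY B-C as a conflict inside the plan: a stop permitted by 10.2.4 leaves 5 participants per df against the minimum of 10 in 10.2.1. That part needs no assumption beyond the plan's own counts.

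The size of the bias is conditional. It assumes that the bound is applied to the paired contrast, that 0.8 is the SD of the difference, and that the planning effect is true. The lower stop probability comes from applying p ≤ 0.0051 to a t-test, the higher from comparing the t-statistic with 2.80. On those terms a stop is a likely outcome, not a remote one. A smaller true effect makes a stop rarer and the overstatement larger.

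For Aims 1-2 the point is weaker: an early stop thins the model and inflates the estimate, but it breaks no stated minimum.

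The documents do not support the view that the bound is miscalculated, that every stopped estimate is too high, or that the adjusted analysis disappears.

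**What to change.** In 10.2.4, and for consistency in 10.1.4, use the half-accrual look for safety and variance only. Delete the efficacy stop, accrue to the stated 40, and use the full 5% at the end.

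If the stop is kept:

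- name the within-person contrast as the analysis that the bound tests;
- state that a 4-df regression after a stop is below the plan's minimum, and limit it to 2 df (insulin dose plus one adjuster);
- report a median-unbiased estimate and interval after a stop.

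The cost is a short amendment, with no one beyond the planned 40. The downside is real: the chance to finish early is lost, so later participants within the 40 undergo clamps, blood draws and, for STUDY 4-7 controls, insulin exposure that a stop would have spared them. Keeping the stop with the three conditions above preserves that benefit, at the price of a smaller adjusted model.
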